6.5 Planned Analyses

6.5.1 Primary Objective Analysis

The primary objective of this study is to quantify sympathetic nervous system (SNS) activity by [¹¹C]MRB PET imaging and microneurography (MSNA). [¹¹C]MRB binding will be quantified in adipose tissue (WAT and BAT), muscle; and whether [¹¹C]MRB binding and sympathetic bursts are altered in individuals with obesity in comparison to individuals with normal weight.

Statistical Analysis: Before statistical testing, all continuous variables will be tested for normality of distribution. Summary statistics will be computed. For between-group comparisons of patient characteristics, two sample t-test or Mann-Whitney U test will be used for continuous variables, and Fisher's exact test for categorical variables. Comparisons of repeatedly measured MSNA will be made using the mixed model analysis. Fixed factors include group and sex and their interactions. Linear contrasts comparing differences between groups or different time points within a group will be estimated.

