Two weeks after visit 4, participants will be asked to return for a separated visit for measurements of SNS activity at rest and after intake of liquid meal. Participants will undergo similar procedures described on visit 4. However, MSNA will be obtained after MMT. The participants will come in the morning (~9am) and will be asked to fast for 10-hour and to maintain their regular exercise routine. A nurse will insert an intravenous (IV) catheter and subjects will ingest a liquid meal (65% CHO, 20% fat, and 15% protein, equal to 40% of daily energy expenditure, per ~16 ounces) to be prepared by the Metabolic Kitchen. Measurements of HR, BP, and EKG (beat-to-beat) will be obtained during the procedure. An intravenous catheter will be inserted into a forearm vein for blood sampling. Following the instrumentation period, resting HR, pulse interval (PI), BP, and MSNA will be recorded for 10 minutes. Following these measurements, plasma will be taken for measurements of insulin, glucose, free fatty acids, norepinephrine, and epinephrine levels. Approximately 40 mL of blood will be drawn at this visit.

HIC 2000030749

Participants will be asked to maintain their regular exercise routine. The order of SNSA Fasting and MMT visits (visits 4 and 5) will be randomized. All study visits will be conducted within an 8-week period (including the two PET and SNSA scans).

Schematic figure of the visits and procedures to be done. The order of the PET scans will be randomized.

Abbreviations: BP=blood pressure, EKG=electrocardiogram, HR=heart rate, MSNA=Muscle sympathetic nerve activity, SNSA=Sympathetic Nervous System Activity

Method of Assignment/Randomization- The order of the PET scan visits 2 (PET-CT Fasting) and 3 (PET/CT-MMT) will be randomly assigned (with a 50% chance of being assigned to each visit). SNSA visits 4 (fasting) and 5 (MMT) will be also be also be randomized (with a 50% chance of being assigned to each visit).

PET and MSNA visits do not need to occur in sequence, i.e. PET scans can occur before or after the MSNA.

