6.1.3 Method of Assignment/Randomization

Method of Assignment/Randomization- The order of the PET scan visits 2 (PET-CT Fasting) and 3 (PET/CT-MMT) will be randomly assigned (with a 50% chance of being assigned to each visit). SNSA visits 4 (fasting) and 5 (MMT) will be also be also be randomized (with a 50% chance of being assigned to each visit).

Blinding and Procedures for Unblinding

N/A

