6.5.2 Secondary Objectives Analyses

- 1) to evaluate whether gender differences affect peripheral SNS in healthy normal weight and obese men and women in adipose tissue (WAT and BAT) and muscle (resting/fasting);
- 2) To investigate the relationship between peripheral and central SNS activity (in obesity, by correlating SNS activity in peripheral tissues (WAT, BAT, and muscle) and brain; and 3) To investigate NET CNS and peripheral SNS activity before and after a high carbohydrate mixed meal in lean and obese men and women.

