6.5.9 Subsets and Covariates

N/A

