6.5.10 Handling of Missing Data

Analyses will be conducted on available data. Adjustments to statistical models will be performed, as appropriate and necessary.

7 Trial Administration

7.1 Ethical Considerations: Informed Consent/Accent and HIPAA Authorization**7.2 Institutional Review Board (IRB) Review**

The protocol will be submitted to the IRB for review and approval. Approval of the protocol must be obtained before initiating any research activity. Any change to the protocol or study team will require an approved IRB amendment before implementation. The IRB will determine whether informed consent and HIPAA authorization are required.

The IRB will conduct continuing review at intervals appropriate to the degree of risk, but not less than once per year.

A study closure report will be submitted to the IRB after all research activities have been completed.

Other study events (e.g. data breaches, protocol deviations) will be submitted per [insert institution's] IRB's policies.

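### The stated contrasts do not include group by condition, which tests for a blunted meal response, and the non-randomised BMI comparison has no age adjustment

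*Combined protocol and SAP*

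**What the plan says.** Sections 6.4.1 and 6.5.1 carry the same analysis paragraph.

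- **Model:** "Comparisons of repeatedly measured MSNA will be made using the mixed model analysis".
- **Terms and contrasts:** "Fixed factors include group and sex and their interactions. Linear contrasts comparing differences between groups or different time points within a group" will be estimated.
- **Two-sample tests:** "For between-group comparisons of patient characteristics, two sample t-test or Mann-Whitney U test will be used for continuous variables".

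Section 6.5.2 restates the third secondary objective, "To investigate NET CNS and peripheral SNS activity before and after a high carbohydrate mixed meal in lean and obese men and women", and gives no method for it. Sections 2.1.2 and 2.2 explain why the meal visits exist: earlier work found smaller food-induced MSNA increments in obesity, and the study will compare the response to a meal between the BMI groups.

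Section 5.3.2 admits ages 18 to 45. No matching on age is described. The entry under "6.5.9 Subsets and Covariates" is N/A. The only text on adjustment is in 6.5.10, under missing data: "Adjustments to statistical models will be performed, as appropriate and necessary". No variable is named there.

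Visit order is randomised for the PET pair and for the MSNA pair (5.1: "The order of SNSA Fasting and MMT visits (visits 4 and 5) will be randomized"; likewise 6.1.3).

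**The concern.** Two questions are left to be settled after the data are seen.

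**Meal response.** The paragraph offers two kinds of contrast: between groups, and between time points within a group. Whether obesity blunts the response is neither of these. It is the difference between the two groups' changes. With only the listed contrasts, the likely report is a significant rise in one group and a non-significant rise in the other, read as blunting. That pattern can easily arise when the true changes are equal.

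**Age.** Participants bring their BMI group with them, so nothing in the design balances age. If the groups differ in age and age is related to norepinephrine transporter binding or MSNA, the unadjusted group difference contains an age effect. Because 6.5.9 is empty and 6.5.10 is open-ended, age could be added or left out once results are known.

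**Working it through.** **1. The plan's own figures.** Section 6.4.2 gives fasting BAT DVR of 1.15 ± 0.19 (lean) and 0.80 ± 0.12 (obese).

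- d = 0.35 / √((0.19² + 0.12²)/2) = 2.20. A two-sided t-test (alpha 0.05 assumed; not stated) needs n = 5.51, so 6 per group for 90% power. This matches.
- The meal calculation, d = (37 − 32)/2 = 2.50, gives 3.76, so 4 per group (80%), and 5.34, so 6 per group (95%). These also match.

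The meal figure concerns energy expenditure in low- versus high-BAT people. Neither calculation addresses the difference in meal response between BMI groups.

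**2. Which contrast answers the meal question.** Write F and M for the fasting and meal means, O for obese and N for normal BMI.

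- Between groups, at one condition: F_O − F_N, or M_O − M_N.
- Within a group: M_O − F_O, and separately M_N − F_N.
- Blunting: (M_O − F_O) − (M_N − F_N). This is group by condition and is not listed.

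To see why the within-group pair is no substitute, assume equal true changes in both groups, independent tests, and within-group power p. The chance that exactly one group is significant is 2p(1 − p): 2 × 0.8 × 0.2 = 0.32 at p = 0.8, and 0.50 at p = 0.5.

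With 20 versus 20, group by condition has 80% power for a difference of 0.91 SD of the within-person change. In outcome SDs this is 0.91 × √(2(1 − ρ)): 1.08, 0.91 and 0.70 for assumed between-visit correlations ρ of 0.3, 0.5 and 0.7.

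**3. Age.** The pilot in 2.1.2 reports 25.6 ± 1.7 years (9 lean women) and 30.8 ± 8.8 years (6 obese women).

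- Gap = 30.8 − 25.6 = 5.2 years; SE = √(1.7²/9 + 8.8²/6) = 3.64; Welch p = 0.21; 95% CI −4.0 to 14.4.
- Age SD: pilot pooled √((8 × 1.7² + 5 × 8.8²)/13) = 5.62; uniform over 18 to 45, 27/√12 = 7.79.
- Standardised gap: 5.2/5.62 = 0.926; 5.2/7.79 = 0.667.

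The bias in the group difference, in outcome SDs, is the standardised gap times the age–outcome correlation r (assumed). The error rate is the noncentral t probability at that bias, 20 versus 20, nominal 5%.

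| r | Bias, age SD 7.79 | Error rate | Bias, age SD 5.62 | Error rate |
|---|---|---|---|---|
| 0 | 0 | 5.0% | 0 | 5.0% |
| 0.1 | 0.07 | 5.5% | 0.09 | 5.9% |
| 0.2 | 0.13 | 7.0% | 0.19 | 8.8% |
| 0.3 | 0.20 | 9.5% | 0.28 | 13.7% |

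This applies to group contrasts. In the group by condition contrast, a constant age effect cancels within each person who has both visits.

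**4. Price of adjusting for age.** From age alone, the variance of the group contrast is multiplied by 1 + gap²/4: 1 + 0.667²/4 = 1.11 and 1 + 0.926²/4 = 1.21. Fitting the full mixed model (ρ = 0.64 assumed, period term included) gives about 1.13 to 1.15 and 1.24 to 1.25, and about 1.03 if ages match. At d = 1.0, power falls from 0.87 to 0.86 (factor 1.03), 0.82 (1.15) or 0.79 (1.25). At d = 2.20 it stays above 0.999.

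**5. Period.** Leaving out a period effect of π SD multiplies the variance of the meal contrast by 1 + π²/(2(1 − ρ)). At ρ = 0.64 and π = 0.2, 0.3 and 0.5 this is 1.06, 1.13 and 1.35. With unblocked order the term itself costs about 1.03, so including it loses about 3% if there is no period effect and breaks even near π = 0.14. The documents give neither π nor ρ.

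**The case against.** The strongest reply is that this is brevity rather than error. The word include does not make a closed list, the outcome is described as repeatedly measured, and within-group time-point contrasts cannot be estimated without a time term. An analyst would add condition. That stands. A reader might infer from group and sex alone (rank 4 over the 8 group by sex by condition cells) that the meal effect cannot be estimated as planned. This follows only if the list is read as exhaustive, and the promised contrasts show it is not. What the reply does not supply is the group by condition contrast: a time term may be implied, but the interactions named are those of group and sex.

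A reader might also infer that the PET endpoints have no analysis. No group test is assigned to them in so many words, but 6.4.2 powers fasting BAT DVR from a two-sided two-sample t-test, which shows the intended comparison. Likewise, 5.1 does not name which MSNA recording is analysed, but its quiet-breathing rule points to the 10-minute rest. Both need a clarifying sentence and neither is an error.

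On age, the gap comes from 15 women and its interval includes zero. The documents show no age–outcome relation, and an eligibility range permits a gap without predicting one. Sex is already in the model, so the plan does not ignore covariates altogether. All of this is fair and limits what can be said about size. It does not remove the case for naming age before the data are seen.

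**Conclusion.** The point holds as two gaps worth closing.

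1. The contrast that tests for a blunted meal response, group by condition, is not stated, and the listed contrasts do not replace it. This follows from the text and needs no assumption.
2. Age is unaddressed in a non-randomised comparison. Its effect is of unknown size. The 5.5% to 13.7% range needs both a recurrence of the imprecise pilot gap and an assumed correlation of 0.1 to 0.3; if either is zero there is no excess.

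Two stronger readings are not supported. Omitting visit order does not bias the meal contrast in expectation, because order is randomised; it costs precision only, by an amount that depends on an undocumented period effect. Nor is any loss of power shown for the group contrast: the documents give no MSNA effect size, and at the plan's d = 2.20, which is for BAT DVR only, power exceeds 0.999 with or without the adjustment.

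**What to change.** - In 6.4.1, 6.5.1 and 6.5.2, state one mixed model for MSNA and for each PET region (BAT, WAT, muscle, hypothalamus, thalamus): group, sex, condition (fasting or mixed meal), group by sex, group by condition, and a random participant effect.
- Name group by condition as the test of the meal response in secondary objective 3.
- Replace N/A in 6.5.9 with age, and report the result without age as a sensitivity analysis.
- While editing, name the fasting/meal condition as the time factor and say which MSNA recording is analysed. A period term may be added or left out, but the choice should be written down.

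The cost is wording. Condition and age are already recorded, and no visit, procedure or sample size changes. Age uses one degree of freedom. The statistical price is the variance increase shown above: negligible if ages match, and at the pilot gap enough to lower power at d = 1.0 from 0.87 to about 0.79 to 0.82.

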6.5.2 Secondary Objectives Analyses

- 1) to evaluate whether gender differences affect peripheral SNS in healthy normal weight and obese men and women in adipose tissue (WAT and BAT) and muscle (resting/fasting);
- 2) To investigate the relationship between peripheral and central SNS activity (in obesity, by correlating SNS activity in peripheral tissues (WAT, BAT, and muscle) and brain; and 3) To investigate NET CNS and peripheral SNS activity before and after a high carbohydrate mixed meal in lean and obese men and women.

6.5.3 Exploratory Objectives Analyses (if applicable)

N/A

6.5.4 Safety

The principal investigator [name] [name] will be responsible for monitoring the data, assuring protocol compliance, and conducting the safety reviews at the specified

HIC 2000030749

frequency, which must be conducted at a minimum of every 6 months (including when reapproval of the protocol is sought). During the review process, the principal investigator will evaluate whether the study should continue unchanged, require modification/amendment, or close to enrollment. Either the principal investigator, the HIC, the NIH (NIDA), or the RSC have the authority to stop or suspend the study or require modifications.

6.5.5 Analysis of Subject Characteristics

The goal of this study is to measure in 20 individuals with normal weight (BMI 18-25 kg/m²) and 20 individuals with obesity (BMI 30-50 kg/m²)

6.5.6 Interim Analysis (if applicable)

N/A

6.5.7 Health economic evaluation

Subjects will paid \$25 for the screening OGTT visit, regardless of the outcome, \$200 for completion of each PET scan sessions (2 in total, \$400), \$100 for completion of each SNSA visit (2 in total, \$200), \$25 for each Mixed Meal Test (2 in total, \$50), and \$100 bonus for completion of all 5 visits.

Subjects will be sent a Bank of America reloadable card that will be sent to their confirmed home address upon completion of each study visit as detailed above. In addition, subjects will be provided with a light lunch on PET day.

2. Costs for Participation (Economic Considerations): Clearly describe the subject's costs associated with participation in the research, and the interventions or procedures of the study that will be provided at no cost to subjects.

No cost to subject related to participation in this research study.

3. In Case of Injury: This section is required for any research involving more than minimal risk, and for minimal risk research that presents the potential for physical harm (e.g., research involving blood draws).

- a. Will medical treatment be available if research-related injury occurs? Yes
- b. Where and from whom may treatment be obtained? Subjects would be assessed by PET Center practitioners and referred as appropriate to medical services.
- c. Are there any limits to the treatment being provided? No
- d. Who will pay for this treatment? Subject or subject's insurance
- e. How will the medical treatment be accessed by subjects? Subjects would be assessed by PET Center practitioners and referred as appropriate to medical services.

Medical treatment will be offered to the subjects for any physical injuries that they receive as a result of participating in this research. However, the subject or his/her insurance company is responsible for the cost. Federal regulations require that subjects be told that if they are physically injured, no additional financial compensation is available.

HIC 2000030749

6.5.8 Other

N/A

6.5.9 Subsets and Covariates

N/A

6.5.10 Handling of Missing Data

Analyses will be conducted on available data. Adjustments to statistical models will be performed, as appropriate and necessary.

7 Trial Administration

7.1 Ethical Considerations: Informed Consent/Accent and HIPAA Authorization**7.2 Institutional Review Board (IRB) Review**

The protocol will be submitted to the IRB for review and approval. Approval of the protocol must be obtained before initiating any research activity. Any change to the protocol or study team will require an approved IRB amendment before implementation. The IRB will determine whether informed consent and HIPAA authorization are required.

The IRB will conduct continuing review at intervals appropriate to the degree of risk, but not less than once per year.

A study closure report will be submitted to the IRB after all research activities have been completed.

Other study events (e.g. data breaches, protocol deviations) will be submitted per [insert institution's] IRB's policies.

7.3 Subject Confidentiality

Required private identifiable information about individuals, such as their medical history, current medications, psychiatric problems, and family history, will be collected by research staff and be used for research purposes and charting after consent is obtained.

HIPAA identifiers:

- Telephone numbers
- E-mail addresses
- Medical record numbers
- All elements of dates (except year) for dates related to an individual, including: birth date, admission date, discharge date, date of death, all ages over 89 and all elements of dates (including year) indicative of such age, except that such ages and elements may be aggregated into a single category of age 90 or older

The data are collected and recorded by trained research personnel. The data will be recorded in Excel spreadsheets that will be saved onto a University encrypted computer or a

HIC 2000030749

secure server, or will be in the form of questionnaires that are filled out by the subject or the researcher. These paper research materials containing confidential information are stored in locked filing cabinets. Additional brain data is collected during the brain imaging scans by trained technologists and is stored on password-protected and encrypted computers with identifying information carefully in compliance with HIPAA regulations.

This research is covered by a Certificate of Confidentiality from the National Institutes of Health. The researchers with this Certificate may not disclose or use information, documents, or biospecimens that may identify you in any federal, state, or local civil, criminal, administrative, legislative, or other action, suit, or proceeding, or be used as evidence, for example, if there is a court subpoena, unless you have consented for this use. Information, documents, or biospecimens protected by this Certificate cannot be disclosed to anyone else who is not connected with the research except, if there is a federal, state, or local law that requires disclosure (such as to report child abuse or communicable diseases but not for federal, state, or local civil, criminal, administrative, legislative, or other proceedings, see below); if you have consented to the disclosure, including for your medical treatment; or if it is used for other scientific research, as allowed by federal regulations protecting research subjects

7.4 Deviations/Unanticipated Problems

If the study team becomes aware of an anticipated problem (e.g. data breach, protocol deviation), the event will be reported to the IRB.

7.5 Data Collection

All digital data will be stored either on a secured server or on University encrypted desktops or laptops. All staff members that come into contact with the data are fully trained to the current HIPAA regulations and are informed as to the proper use of all data. Identifiable paper information is kept in locked file drawers and password protected computer files. Results are published as group data without the use of characteristics that would identify individual subjects. We quote information only by number in conference discussions, scientific reports, or publications, in order to maintain anonymity. Identifiable research data, including recruitment and screening information and code keys, are stored on a secure database located on the internal PET Center Network. The PET network is protected by a Cisco PIX firewall operated by ITS. All research data are backed up nightly to a Dell PV-136T library with 4 IBM Ultrium-TD2 tape drives using the backup software Legato Networker 7.3 from EMC. Human subjects enrolled in the study are assigned a subject-specific random identifier. Subject identifiers and the means to link the subject names and codes with the research data are stored in separate locations within the database. The software of the database limits the ability to connect the random identifier to the actual subject identification information to research team members only. Access to the database is password protected and each research team member is required to have a unique ID and password to gain access to the database. Authorized users employ their netid and authentication is performed using Yale's central authentication server. Users always access research data through the random identifier only. Direct identifiers belonging to subjects who withdraw from the study, will be stripped from the key.

The data will be stored in locked filing cabinets and on the password-protected secure database on the internal Yale University PET Center Network for at least 7 years after the close of the study, accessed only by authorized personnel. After 7 years, the data will be de-identified. Data may be kept indefinitely.

HIC 2000030749

7.6 Data Quality Assurance

See 6.5.4

7.7 Study Records

- Regulatory Documents
- EKG
- Consent Forms
- Subject Medical Records
- PET imaging data (and related scan day paperwork)
- Biospecimens (and related lab request paperwork – e.g. blood insulin measurements)

7.8 Access to Source Documents

See 7.5

7.9 Data or Specimen Storage/Security

See 7.5

